3.1 Rationale

Exenatide is an injectable glucagon-like peptide 1 (GLP-1) receptor agonist approved as an adjunct to diet and exercise to improve glycemic control in adults with type 2 diabetes mellitus (T2DM) by the United States and Europe. Byetta (exenatide twice daily) is administered as a subcutaneous injection within 1 hour before the two main meals of the day, approximately 6 hours or more apart. Treatment is typically initiated at 5 mcg per dose, twice daily, and may be increased to 10 mcg twice daily based on the patient’s clinical response.

During Health Canada’s review of the marketing authorisation application of exenatide, Lilly provided a commitment to monitor the off-label use and compliance to the Summary of Product Characteristics (SPC) of exenatide prescriptions through a post-launch utilization study. Specifically, Health Canada requested that:

The RMP should be revised to include a post-marketing study conducted on exenatide use and adherence to labeling recommendations in Canada, similar to the drug utilization study requested by the EU Regulatory authority that is currently ongoing in various EU countries. Since preliminary information has already indicated off label use of exenatide with either TZD or insulin in the EU, the need for further study and/or additional risk management actions with these products should be specifically addressed.

Table 1: Canadian Byetta Indication

Byetta Monograph
Indication and Clinical Use:
BYETTA is indicated in combination with metformin and/or sulfonylurea to improve glycemic control in patients with type 2 diabetes mellitus, when maximally tolerated doses of these oral therapies in addition to diet and exercise do not provide adequate glycemic control.
BYETTA is indicated in combination with insulin glargine (with or without metformin) to improve glycemic control in patients with type 2 diabetes mellitus when insulin glargine (with or without metformin) in addition to diet and exercise, does not provide adequate glycemic control
Contraindication:
BYETTA should not be used in the pediatric patient population.

BYETTA should not be used in patients with end-stage renal disease or severe renal impairment (creatinine clearance <30 mL/min), including patients receiving dialysis

BYETTA is contraindicated in patients with diabetic ketoacidosis, diabetic coma/precoma or type 1 diabetes mellitus.

Source: Byetta Drug Product Monograph, Canadian Pharmacists Association, online version, April 2011.

3.2 Objectives

IMS Brogan will conduct a study to assess Byetta use and adherence to the Canadian indications and clinical use recommendations since its launch in the Canadian market.

3.2.1 Primary Objectives

To evaluate exenatide use outside labeling indications in Canada.

3.2.2 Secondary Objective

To assess the concomitant use of exenatide with either thiazolidinediones (TZDs) or insulin.

3.3 Data Source

The proposed study will utilize data from the IMS Brogan's Longitudinal Patient Data assets (LRx). LRx tracks the prescription activity of anonymized patients over time (longitudinally), with records dating back to 2004. Collection of prescriptions that include anonymized patient data from approximately 4,000 pharmacies nationwide enables visibility to all payer types and is ideally suited to provide insights into chronic, retail-based markets. LRx data is un-projected and is based on a large sample (~75% coverage nationally, see table 1). By tracking patient prescription history, LRx goes beyond measuring prescription volumes to tracking real-world behaviour and use.

Table 2: Coverage of LifeLink (LRx) Patient Longitudinal Database

Region	% Coverage
	As a % of projected Rx volume in CompuScript – MAT Dec 2011
Total Canada	74.6%
British Columbia	66.4%
Alberta	68.8%

Saskatchewan	71.9%
Manitoba	79.6%
Ontario	75.8%
Quebec	76.7%
New Brunswick	95.7%
Nova Scotia	67.2%
Newfoundland / PEI	53.1%

3.4 Study Overview

3.4.1 Assumptions

[figure not shown]
IMS data in Canada does not contain diagnosis codes, therefore disease indications will be inferred from pattern of drug treatment. We assume that pattern of drug treatment predicts indication and identifies Type 2 diabetes patients. For example, a patient who receives no OADs prior to insulin treatment would be classified as Type 1 Diabetes, while a patient who receives an OAD at any point in time would be classified as Type 2 Diabetes. We also assume the molecules used in the Diabetes market definition are used exclusively for diabetes treatment and we will not consider off-label use (e.g.. metformin for treatment of polycystic ovary syndrome. This use is expected to be very small.).

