3.4.3 Study Population

Inclusion/Exclusion Criteria:

All patients in the LRx database who have been prescribed Byetta in Canada during the analysis period will be included in the study. Patients with inconsistent records and/or insufficient data, as shown in table 3, will be omitted to restrict the analysis to a consistent and robust patient sample.

Exclusion criteria are required since the pharmacy data (LRx) is driven through data entry at the individual stores. The criteria are used to filter out transactions that either have entry mistakes or have place-holder information that is not accurate. The exclusion criteria are established to ensure a consistent record for patients in the study sample. Inclusion and exclusion criteria may be modified during the initial stages of the project.

Table 3: Exclusion criteria applied to remove patients with inconsistent Rx history

Criteria	Conditions for Exclusion	Rationale
Demographic Criteria	Patients without a consistent year of birth, province, or gender	Patients without a consistent demographic record of gender, year of birth and province are not reliable due to inconsistencies
Constant Store Criteria	Patients at stores with inconsistent reporting after May 2011	Stores with inconsistent recorded information will not have accurate information on what prescriptions a patient received
Max Rx Criteria	Patients with more than 208 Rx/year	This is to eliminate pharmacist error
Min Rx Criteria	Patients with fewer than 6 Rx	Patient with less than 6 prescriptions are excluded because there is the potential for including the same patient multiple times as occasionally patients fill prescriptions at different pharmacies when traveling or for convenience
Consistent Patients	Remove patients without any prior Rx at a store	Removing patients without any other prior prescriptions at a store also eliminates patients who have changed pharmacies and may be included multiple times in the data
Analysis Period	Remove patients without any	Patients who do not have a prescription

	Rx in the Analysis Period	in the analysis period cannot be included as they do not have any prescriptions to analyze
12 Month Gap	Remove patients with a year gap between Diabetes Rx	Patients with a year gap between diabetes prescriptions are likely to have filled prescriptions at an alternative pharmacy and could be counted multiple times in the data set

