3.4.4 Study Outcomes and Definitions

[figure not shown]
The primary outcome of interest is the off label use of Byetta in Canada.

A patient's therapy type will be inferred by identifying if a patient switches between, or adds on to therapies, as shown in figure 3.

Mono Therapy is defined as a patient receiving a specific therapy (Therapy 1) prior to a different therapy (Therapy 2) where Therapy 1 is not detected after Therapy 2 initiation. Mono therapy for this study, refers to a patient received a prescription for only one product at a given time.

Concomitant Therapy is defined as a patient receiving a specific therapy (Therapy 1) prior to a different therapy (Therapy 2) where Therapy 1 is detected after Therapy 2 initiation.

Figure 3: Distinguishing between add-on and switch therapies

Patients will be selected for the study if they receive a Byetta script anytime during the analysis period and if they met the inclusion criteria. To identify on-label vs. off-label use, patient history will then be used to classify patients as "inferred on-label" if they also received Metformin and/or SU or Lantus during the study (Business rules 1 and 2 in Table 5).

All other patients that do not meet the criteria for use of Byetta with metformin and/or SU or Lantus will be classified as “inferred off-label”. The group of patients classified as “inferred off-label” will then be further classified to gain a better understanding of the trends in “inferred off-label” use of Byetta (Business rules 3-10 in Table 5).

The Business rules described in Table 5 are prioritized to ensure the appropriate classification of each patient. Therefore patients will be classified based on the highest rank business rule. For example, if a patient receives scripts for both Metformin and other insulin during the analysis period, they will be classified as “inferred on-label” as they have a script for metformin and therefore are classified by business rules 1 and 2

Note: The patient classification categories (‘Inferred Adherence Label’) can be modified in the initial phase of the project.

Table 5: Business rules applied to classify patients as “on-label” vs. “off-label”

(The business rules have been structured to align with the Canada monograph for Byetta indication and clinical use (see Table 1) and will be finalized upon study initiation).

Rank	Business Rules	Cohort Description	Inferred Adherence Label

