1	Concomitant use of* Byetta with metformin (met) and/or sulfonylurea (SU), OR Concomitant use of Byetta with Lantus	Met and/or SU or Lantus is prescribed with Byetta	Inferred On-label
2	Evidence of** Byetta and metformin and/or sulfonylurea OR Evidence of Byetta and Lantus	Met and/or SU or Lantus is not prescribed with Byetta, but both appear in the analysis period	Inferred On-label
3	Evidence of Byetta and Levemir	Levemir is prescribed in the analysis period	Off-Label Insulin Use
4	Evidence of Byetta and Human Basal Insulin	Human basal insulin is prescribed in the analysis period	
5	Evidence of Byetta and thiazolidinedione (TZD)	TZD is prescribed in the analysis period	Off-Label OAD Use

6	Byetta Alone	No other products prescribed in the analysis period	Inferred Off-label
7	Evidence of Byetta and all other insulin	Other insulin is prescribed in the analysis period	
8	Evidence of Byetta and all other OADs	Other OADs are prescribed in the analysis period	
9	Pediatric Patients	Patient is under the age of 18 (<18)	
10	All other combinations	All other combinations	

Note: Evidence of Diabetic ketoacidosis, diabetic coma/precoma and end stage renal disease cannot be inferred from the dataset; therefore we will not be able to identify these patients as a separate group

* "Concomitant use of..." refers to continued use of Byetta and other product

** "Evidence of..." refers to anytime within the study period including look-back or look forward periods

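### No Table 3 exclusion or Table 5 rule uses the Type 1 inference in Section 3.4.1, so Byetta with Lantus and no OAD counts as on-label; this can under-estimate off-label use, whereas the Limitations name only over-estimation

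*Protocol*

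**What the plan says.** Four parts of the protocol bear on this.

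- **Section 3.4.1 (Assumptions).** There are no diagnosis codes, so indication is inferred from treatment pattern. Two examples are given: "a patient who receives no OADs prior to insulin treatment would be classified as Type 1 Diabetes", and "a patient who receives an OAD at any point in time would be classified as Type 2 Diabetes".
- **Section 3.1, Table 1.** On contraindications: "BYETTA is contraindicated in patients with diabetic ketoacidosis, diabetic coma/precoma or type 1 diabetes mellitus". On the insulin combination: "BYETTA is indicated in combination with insulin glargine (with or without metformin) to improve glycemic control in patients with type 2 diabetes mellitus", where glargine does not give adequate control.
- **Section 3.4.3.** "All patients in the LRx database who have been prescribed Byetta in Canada during the analysis period will be included in the study", subject to the exclusions in Table 3. Those concern record consistency, prescription counts, gaps and available history. None concerns diabetes type.
- **Section 3.4.4, Table 5.** Rule 1 includes "Concomitant use of Byetta with Lantus" and rule 2 includes "Evidence of Byetta and Lantus". Both give the label Inferred On-label, and neither sets a condition on OADs or diabetes type. On priority: "Therefore patients will be classified based on the highest rank business rule".

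Section 3.4.7 (Limitations) says on-label and off-label status is an estimate. The only direction of bias it names is over-estimation of off-label use, on the ground that the on-label rules are strict.

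**The concern.** The primary objective is use outside the labelled indications, under a commitment made during Health Canada's review. Type 1 diabetes is a labelled contraindication for which the protocol itself describes a prescription-based proxy. The proxy then plays no part in the classification or in the results tables.

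The consequence is not neutral. For one group, the rules give the label opposite to the one that Section 3.4.1 and Table 1 together imply. That group sits in the on-label count, so any error lowers the primary off-label percentage. A reader who relies on the Limitations would take the reported figure as a conservative ceiling, and for this group it is not. Insulin co-use is also part of the secondary objective, so the affected patients belong to a population the study was asked to describe.

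**Working it through.** The protocol states no figure for this point and no error rate or sample size bears on it, so the check is a trace through the rules.

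**Step 1: who is inferred Type 1.** Take Byetta patients with insulin and no OAD at any time. They meet the first example in Section 3.4.1 and cannot meet the second.

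**Step 2: are they excluded?** No. Table 3 has no criterion on diabetes type.

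**Step 3: where Table 5 puts them.** With no OAD they cannot meet the metformin or sulfonylurea part of rules 1 and 2, nor rule 5 (TZD) or rule 8 (other OADs). They have insulin, so rule 6 (Byetta alone) does not apply. That leaves:

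| Insulin on record, no OAD | Rule reached | Label |
|---|---|---|
| Lantus, alone or with any other insulin | 1 or 2 | On-label |
| Levemir, no Lantus | 3 | Off-label |
| Human basal, no Lantus or Levemir | 4 | Off-label |
| Rapid or premix only | 7 | Off-label |

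The last three groups fall off-label because of the insulin product, not because of diabetes type, so the on/off split would not change for them. Only the Lantus row conflicts with Section 3.4.1 read with Table 1. Because the highest-ranked rule decides, no later rule can correct it.

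**Step 4: effect on the primary percentage.** Let N be all classified patients, A those off-label under Table 5, and L those on Byetta and Lantus with no OAD on record.

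- L counted on-label (Table 5 as written): A / N.
- L counted off-label (Section 3.4.1 with Table 1): (A + L) / N.
- Difference: L / N.

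The difference is zero if there are no such patients and cannot exceed the on-label share, (N − A) / N. The protocol gives none of N, A or L (Section 3.4.5 calls Byetta use in the first year unknown), so the range cannot be narrowed from the document.

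**Step 5: direction.** Since (A + L) / N is never below A / N, any error from this group is downward. Section 3.4.7 does not mention it.

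**The case against.** The strongest reply is that rules 1 and 2 follow the labelled combination. Table 1 allows glargine without metformin in type 2 diabetes, so a Lantus user with no recorded OAD may be a labelled patient. Capture is also incomplete: national coverage is 74.6% (Table 2), and Table 3 acknowledges that patients fill at other pharmacies, so OADs can be missed. This stands. It rules out saying that every such patient is misfiled, and it argues against simply moving the whole group to off-label in the primary result. It does not remove the conflict, because Section 3.4.1 gives the proxy without reservation.

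Two further readings are tempting but not supported.

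- A reader might infer that Type 1 was meant to be identified, because the note under Table 5 omits it from the contraindications that cannot be inferred. But that list also omits severe renal impairment, which Table 1 names, and Section 3.4.7 introduces its own list as examples. The lists are not exhaustive and show no intent.
- A reader might infer that the two examples in Section 3.4.1 contradict each other for a patient given insulin first and an OAD later. The natural reading is that any OAD means Type 2, and the overlap changes no Table 5 result, because no rule uses diabetes type.

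It can also be said that Table 5 is to be finalised at study initiation and that a figure in Section 3.4.1 is not shown. Both are true, but no available text applies the inference or promises a rule for it. The general statement that diagnosis is only inferred does not disclose this gap or its direction.

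**Conclusion.** The point holds as an internal inconsistency affecting the primary outcome. Section 3.4.1 and Table 1 together make Byetta with insulin and no OAD a contraindicated use by inference; Table 5 counts the Lantus part of that group as adherent. Off-label use can therefore be under-estimated by up to L / N, a quantity the documents do not give.

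This rests on reading the first example in Section 3.4.1 as the working proxy for Type 1 and on any OAD meaning Type 2. It does not establish that the affected patients truly have Type 1 diabetes, nor that they are numerous. It does establish that the one-sided statement of bias in the Limitations is incomplete, and that the study as planned could not show how much the answer depends on this group.

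**What to change.** Reconcile Section 3.4.1, Table 1, Table 5 and Section 3.4.7 before data are extracted.

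1. Define a flag, inferred Type 1: insulin on record and no OAD at any point in the patient's available record. State that an OAD at any time means Type 2.
2. Report the flag as its own row in Table 6, by gender like the other rows. It cuts across the existing categories, so mark it as a subset row and show the Lantus part separately.
3. Give the off-label percentage twice: with the Lantus, no-OAD group counted on-label (lower bound) and counted off-label (upper bound). State that these are bounds for this one source of error only.
4. Amend the Limitations to say that counting this group on-label biases off-label use downward, alongside the over-estimation already described.

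The cost is one flag, one table row and a second percentage from the same data. The drawback is that the upper bound will include some true Type 2 patients whose OADs were not captured, and the text should say so. If the sponsor considers the proxy too weak to use, Section 3.4.1 should say that Type 1 cannot be reliably inferred, and the Limitations should list it; the count in item 2 would still be worth reporting.

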3.4.2 Study Design

This will be a retrospective database study using IMS Brogan's LRx dataset, in which de-identified patient level prescription information will be used to evaluate adherence to the labeling recommendations for exenatide use in Canada. The study will be based on a 'Look-Back,' 'Analysis' and 'Follow-Up' period as shown in figure 1. Patients will be selected for the study if they are receiving a Byetta prescription in the 12 month analysis period.

[figure not shown]
The 'Look-back' period is used to ensure that each patient within the analysis period has at least 6 months of data prior to first Byetta script. This eligibility period ensures that a patient whose first Byetta script occurs at the start of the analysis period can be classified appropriately and that they are present in the database prior to the first script. Similarly, the 'Follow-up' period is used to ensure that each patient has at least 3 months of data following the last script within the analysis period. This ensures that the duration of therapy for a patient who receives their last script at the end of the analysis period is accounted for and can have their therapy appropriately classified, specifically around the concomitant use of Byetta with insulin or TZDs.

Figure 1: Study periods proposed for analysis of Byetta use in the 1st year post launch

In addition to the study period proposed in figure 1, the analysis will be conducted for Year 1, 2 and 3 post Byetta launch allowing for an analysis of trends in Byetta use over time, as shown in figure 2. Study 1* will provide results on Year 1 and 2 and would commence at the availability of Aug 2013 data. Study 2** will provide Year 3 results and would commence at the availability of Aug 2014 data.

Figure 2: Three proposed analysis periods for study post Byetta Launch

Note: Implies that the look-back period and the follow-up period are at least 6 months and 3 months for each patient, respectively.

Note: Month 1 = Date of First Byetta Sale = June 2011

*Study 1: All Byetta prescriptions in the database in months 0-24, post launch

** Study 2: All Byetta prescriptions in the database in months 25-36, post launch

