6-month look back data	Remove patients without 6 months of data prior to first Byetta script	Ensures all patients are present in the dataset and have a consistent record for analysis
3-month Follow-up data	Remove all patients without 3 month follow-up data	Ensures patients therapy can be appropriately classified as add-on or switch

To identify other diabetes therapies for the selected patients, prescriptions for product groups in table 2 will also be tracked for selected patients

Table 4: Diabetes therapies tracked for Byetta patients

Category	Product Group	Product
Insulin	Premix Human	Lilly Human Premix, NNCI Human Premix
	Premix Analog	Humalog Mix, NovoMix
	Basal Human	Novolin NPH, Humulin N
	Basal Analog	Lantus, Levemir
	Rapid Human	Humulin R, Novolin Toronto
	Rapid Analog	Apidra, Humalog, NovoRapid
OAD	Metformin	Metformin
	Sulfonylurea (SU)	Diamicon / Diamicon MR, Gliclazide, Glimepiride/ Amaryl, Glyburide
	Thiazolidinedione (TZD)	Avandamet, Avandaryl, Actos, Avandia, Generic Pioglitazone
	PPG Regulators	GlucNorm, Starliz, Generic Repaglinide
	DPP4	Januvia, Onglyza, Janumet, Trajenta

	Prandase	Prandase
GLP1	GLP1	Victoza, Byetta

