3.4.5 Sample Size

All patients in the LRx database who have been prescribed Byetta in Canada during an analysis period and met the inclusion criteria will be included in the study. In similar studies in this market ~500,000 patient records have passed selection criteria for inclusion to a study sample. However the anticipated use of Byetta amongst this patient population in the first year of marketing in Canada is unknown at the present time and is projected to be modest. Upon initiation of the study, IMS Brogan will analyze the dataset to identify the number of patients available for study (the number of patients on Byetta in the analysis period). The number of Byetta patients is expected to rise in each year analyzed.

To allow for sufficient patients for a robust analysis, we will perform the first study 2 years after Byetta's launch in Canada, analyzing the two years separately (see figure 2). The analysis will be repeated in the subsequent year, to capture additional Byetta patients and identify shifts in Byetta usage.

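### Year 1 holds only Byetta starters while Years 2 and 3 mix starters with continuing users, so the planned trend cannot separate a change in prescribing adherence from a change in who stays on the drug.

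*Protocol*

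**What the plan says.** Section 3.4.2 sets the time origin: "Month 1 = Date of First Byetta Sale = June 2011". It selects on any use in the year: "Patients will be selected for the study if they are receiving a Byetta prescription in the 12 month analysis period". Section 3.4.3 repeats the rule ("All patients in the LRx database who have been prescribed Byetta in Canada during the analysis period will be included in the study"), and so does section 3.4.4 ("Patients will be selected for the study if they receive a Byetta script anytime during the analysis period"). For Year 3, the footnote to Figure 2 takes "All Byetta prescriptions in the database in months 25-36, post launch", which includes refills by patients who started earlier.

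No exclusion in Table 3 removes earlier starters. The look-back criterion reads "Remove patients without 6 months of data prior to first Byetta script". It asks for presence in the database before the first Byetta script, not for Byetta-free time before the analysis year.

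The years are meant to be compared. Section 3.4.2 describes the three periods as "allowing for an analysis of trends in Byetta use over time", and section 3.4.5 repeats the analysis "to capture additional Byetta patients and identify shifts in Byetta usage". Section 3.4.6 stratifies the results by gender, and the Table 6 shell has no other split.

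**The concern.** Launch falls at the start of Year 1, so the make-up of the user population changes by construction between Year 1 and the later years. Continuers are patients who stayed on the drug. If staying is related to label status, the off-label share among them differs from that among starters, and the yearly figure moves even when new prescribing does not change.

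This matters because the study's title concerns compliance with prescribing guidelines, and section 3.1 traces it to a commitment to Health Canada to monitor off-label use and compliance of exenatide prescriptions. A falling off-label share would naturally be read as better adherence by prescribers, and a rising one as a reason for further risk management. The planned tables would not show whether either reading is justified.

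Section 3.4.7 acknowledges that patients who start early or late in an analysis period contribute different amounts of data. It does not mention the change in user mix from one year to the next.

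**Working it through.** The protocol gives no off-label rate, persistence rate or expected number of Byetta patients, so there is no stated figure to reproduce. The check has a structural part, which comes from the text, and a numerical part, which rests on assumed rates.

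**Structure (from the protocol).** First sale is in Month 1, so the share of continuers is c = 0 in Year 1. Any script in the year qualifies and earlier starters are not excluded, so c > 0 in Years 2 and 3 whenever anyone persists.

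**Formula.** Let p_new be the off-label share among starters and p_cont the share among continuers.

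- Year 1 share = p_new
- Later-year share = (1 − c) × p_new + c × p_cont
- Shift from Year 1, with p_new constant = c × (p_cont − p_new)

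**Range, with p_new assumed constant at 20%:**

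| p_cont | c = 20% | c = 40% | c = 60% |
|---|---|---|---|
| 10% | 18% (−2 points) | 16% (−4) | 14% (−6) |
| 20% | 20% (0) | 20% (0) | 20% (0) |
| 30% | 22% (+2) | 24% (+4) | 26% (+6) |

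**Illustration over three years.** Assume 80 on-label and 20 off-label starters each year, fixed continuation rates from one year to the next, and no change of label status within a patient.

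*On-label 60% continue, off-label 30%:*
- Year 1: 20/100 = 20.0%
- Year 2: on-label 80 + 0.6 × 80 = 128; off-label 20 + 0.3 × 20 = 26; share 26/154 = 16.9%
- Year 3: on-label 80 + 0.6 × 128 = 156.8; off-label 20 + 0.3 × 26 = 27.8; share 27.8/184.6 = 15.1%

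*On-label 30% continue, off-label 60%:*
- Year 1: 20.0%
- Year 2: on-label 80 + 0.3 × 80 = 104; off-label 20 + 0.6 × 20 = 32; share 32/136 = 23.5%
- Year 3: on-label 80 + 0.3 × 104 = 111.2; off-label 20 + 0.6 × 32 = 39.2; share 39.2/150.4 = 26.1%

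*Equal continuation:* continuers are 20% off-label as well, so every year reads 20%.

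**Cross-check with the formula.** In Year 2 of the first case there are 48 + 6 = 54 continuers, so c = 54/154 = 35.1% and p_cont = 6/54 = 11.1%. The shift is 0.351 × (11.1 − 20) = −3.1 points, which gives 16.9%.

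In all three cases the off-label share among starters is 20% every year. Reporting starters separately sets c = 0 and removes the shift.

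**The case against.** The strongest reply is that the objectives in section 3.2 concern use, and the planned trend is a trend in use. If off-label users stop and on-label users stay, off-label use has fallen. That is a true change in the quantity named, and refills are still prescriptions. This stands as far as the yearly figures go: all-user prevalence is a legitimate measure. It does not license a statement about prescribing adherence from the same figures, and the study's title and regulatory origin invite that statement.

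A second reply is that extra table rows are usually left to a statistical analysis plan, and that sections 3.4.3 and 3.4.4 allow the criteria and categories to be modified at the start. However, this protocol itself fixes the population, the stratification and the table shells, so the limit on what the trend can show is already set here. The room to modify makes the change easy.

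A third reply is that the illustrated persistence gap is invented and could be zero. That is correct. The figures show what is possible, not what is expected.

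Three stronger readings are tempting, and the documents do not support them:

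- *Patients are double-counted.* Section 3.4.5 analyses the first two years separately, and section 3.4.6 completes the tables for each study year. A patient counted once in each year's prevalence is counted correctly.
- *Continuers have more data for the any-time evidence rules, and so drift on-label.* This depends on whether the look-back is anchored to the first-ever script or to the analysis year. The text does not settle it and the figures are not shown. With the second anchor, metformin taken only before Byetta could drop out of view and push continuers the other way. The mixture effect needs neither reading.
- *Section 3.4.7 implies a new-user design, because it speaks of patients initiating Byetta within the period.* No criterion imposes one.

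**Conclusion.** The point holds as a limit on how differences between years may be read, not as an error in any single year's result. The change in user mix follows directly from the launch date and the selection rule. Whether it moves the off-label share depends on whether continuers and starters differ in that share, and the protocol gives nothing from which to judge this. Under the assumed rates the apparent three-year movement runs from −4.9 points (20.0% to 15.1%) through zero to +6.1 points (20.0% to 26.1%), with no change in prescribing to starters. These figures rest on constant starter numbers, a constant 20% off-label share among starters, fixed continuation rates and stable label status. The change is a worthwhile, cheap improvement if any trend in prescribing adherence is to be reported to the regulator.

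**What to change.** Keep the all-user results in Table 6 as planned. For Years 2 and 3, add:

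- results for patients whose first-ever Byetta script falls in that year;
- results for patients continuing from an earlier year;
- the number of patients who appear in more than one year.

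State in section 3.4.6 that any conclusion about trends in prescribing adherence rests on the starter results (Year 1 is already all starters), and that the all-user series describes a trend in prevalent use. Add the change in user mix to section 3.4.7.

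No new data are needed, because the look-back criterion already requires the date of the first Byetta script. The real cost is smaller cells: section 3.4.5 expects modest use, and Table 6 already crosses four categories with gender. Where cells are sparse, the starter and continuer results can be pooled over gender, with the all-user results by gender left unchanged.
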